5.2 Rationale for Dosing

In clinical studies in healthy volunteers, obicetrapib was generally well tolerated in single doses up to 150 mg and multiple doses up to 25 mg/day for 21 days. In clinical studies in patients, obicetrapib was also well tolerated after daily dosing of 10 mg for 12 weeks, both alone and in combination with 2 different statins. Near maximal effects were observed with the 10 mg obicetrapib dose. At this dose level, CETP activity was reduced, HDL-C levels were increased, and LDL-C levels were decreased. There were no dose-related AEs identified and no clinically significant changes in vital signs, ECGs, or hematology or biochemistry parameters in any clinical studies. A statistically significant reduction in Lp(a) levels from baseline was also observed at the 10 mg obicetrapib dose level. Therefore, the present study will utilize a dose of 10 mg obicetrapib in participants with HeFH and/or a history of ASCVD or multiple ASCVD risk factors who are not adequately controlled by their maximally tolerated lipid-modifying therapy.

The ezetimibe dose of 10 mg is the current FDA-approved dose.

5.3 Randomization and Blinding

Participants who meet all inclusion criteria and none of the exclusion criteria will be randomized at Visit 2 (Day 1) via the Interactive Response technology (IRT) system a 1:1:1:1 ratio to receive FDC therapy, obicetrapib monotherapy, ezetimibe monotherapy, or placebo as described in Section 5.1.

Approximately 70% of the participants enrolled into this study should be taking HIS. No more than approximately 10% of participants in this study will be completely statin intolerant.

Participants without underlying HeFH or a history of ASCVD but with multiple ASCVD risk factors will comprise a maximum of 30% of the total participants enrolled into the study. Participants with only HeFH will comprise a maximum of 20% of the total participants enrolled into the study.

Participants, the Sponsor, Investigators, and all study site personnel involved in the study, including personnel carrying out study procedures, evaluating participants, entering study data,

and/or evaluating study data, will remain blinded to treatment allocations until all participants have completed all study-related visits and assessments and the database has been locked for analysis.

Participants, Investigators, the Clinical Research Organization, and the Sponsor will be blinded to all lipid results from Day 1 (Visit 2) for the first participant until the database is locked in order to protect blinding to treatment assignment.

Active and placebo products will be identical as described in Section 5.5.1. Medication kits with a unique code will be assigned to participants at various points in the study by the IRT system.

5.4 Breaking the Blind

Study drugs will be managed using the IRT system. Each user will have a unique username and passcode to access the system. Investigators shall not break the study blind during the study, and Investigators should treat all participants as if they had received obicetrapib or ezetimibe. However, in situations in which knowledge of the participant's study drugs is necessary for clinical management, the Investigator should proceed with unblinding.

Once a participant's treatment assignment has been unblinded, the Medical Monitor or designee should be notified within 24 hours of unblinding of the treatment. Information relating to unblinding (eg, date and time of the call to the Medical Monitor by the Investigator, reason for unblinding, and date and time of unblinding) shall be clearly recorded in the participant's study file and in the electronic data capture (EDC) system, as part of relevant standard operating procedures. In addition, the Investigator should consider whether the clinical event prompting unblinding should be considered an AE or SAE, according to the regulatory definitions or criteria for AEs or SAEs, and if so, submit an AE/SAE report to the Sponsor or designee (see Section 8.3). The Sponsor or designee will also unblind any SAE reports that are unexpected and considered to be related to the study drugs, in accordance with safety reporting guidance and regulations.

Each study site will be provided with a sealed envelope containing a 6-digit code that can be entered into the IRT system to unblind a participant's treatment assignment.

5.5 Drug Supplies

5.5.1 Formulation and Packaging

The study drugs consist of obicetrapib 10 mg + ezetimibe 10 mg FDC tablets, obicetrapib 10 mg tablets, ezetimibe 10 mg capsules (over-encapsulated 10 mg tablets), and matching placebo for each. All study drugs are manufactured in accordance with current Good Manufacturing Practice.

Obicetrapib 10 mg + ezetimibe 10 mg FDC tablets are white to off-white, round, film-coated tablets with no identifying markings, containing 10 mg of obicetrapib (as obicetrapib calcium drug substance) and 10 mg of ezetimibe drug substance.

Obicetrapib tablets are round, white film-coated tablets, with no identifying markings, containing 10 mg of obicetrapib (as obicetrapib calcium drug substance).

Ezetimibe capsules are ezetimibe 10 mg tablets (Ezetrol®) filled into capsule shells, 1 tablet per capsule. Each capsule also contains lactose monohydrate, an excipient material common to the tablets, as a filler to prevent the tablet from rattling in the capsule shell.

Placebo tablets for the FDC are matching round, white film-coated tablets, with no identifying markings.

Placebo tablets for obicetrapib are matching round, white film-coated tablets, with no identifying markings. The excipients present in the tablet cores are microcrystalline cellulose, mannitol, sodium starch glycolate, colloidal silicon dioxide, and magnesium stearate. A commercially available film-coating formula (Opadry II white, ex Colorcon) is applied to the cores.

Placebo capsules for ezetimibe are the identical capsule shells filled with the excipient filler material, lactose monohydrate (no tablets). Additionally, magnesium stearate is added to the filler.

All study drugs will be packaged into kits providing the 3 study drugs (2 tablets and 1 capsule) for each treatment group. The kits will be clearly labelled to indicate which tablets and capsule to use on each day. Each individual kit will provide a sufficient supply for 28 days of dosing, with enough for an extra 8 days of dosing. The shelf-life will be assigned based on the stability of the individual study drugs and will not be greater than the expiry date of the input ezetimibe tablets. The kits will be stored at room temperature, no higher than 77°F (25°C), protected from moisture.

The physical, chemical, and pharmaceutical formulation properties and characteristics of the obicetrapib 10 mg + ezetimibe 10 mg FDC and obicetrapib tablets are described in the Investigator's Brochure.

All study drugs will be labelled in accordance with all applicable local regulatory requirements.

5.5.2 Study Drug Preparation and Dispensing

At Visit 2 (Day 1), participants will receive 1 kit (containing 36 FDC tablets or matching placebo tablets, 36 obicetrapib tablets or matching placebo tablets, and 36 ezetimibe capsules or matching placebo capsules totaling 108 tablets/capsules per kit) with the study drugs appropriate for the participant's treatment group. At Visit 3 (Day 28), participants will receive 2 kits as described above. The 2 kits provide sufficient supplies for 56 days of dosing, with enough for an extra 16 days of dosing in case the participant needs to postpone Visit 4 (Day 84). Each individual kit will provide a sufficient supply for 28 days of dosing, with enough for an extra 8 days of dosing. Participants will be instructed to take 3 units from the kit each day. The kit will be clearly labelled to indicate which tablets and capsule to use on each day. Participants will be instructed to bring all unused study drugs to the site at the next visit.

This study protocol includes contingency measures to manage disruptions due to COVID-19 control measures, including modifications to dispensation of the study drugs specific to situations where COVID-19 is impacting study conduct. See Section 3.1.4 for details of COVID-19 contingency measures. In the absence of a COVID-19 impact, it is expected that Investigators and participants follow the protocol requirements as set forth.

5.5.3 Study Drug Administration

Study drugs (2 tablets and 1 capsule) will be administered by the participant orally with water, with or without food, once daily on Day 1 to Day 84 at approximately the same time each morning. On days with visits scheduled, participants should not take the study drugs prior to the visit but should bring the study drugs with them to the site. The study drugs will be administered with water following all fasted blood samples. At Visit 3 (Day 28) and Visit 4 (Day 84), participants will dose from the kit received at the previous visit (Visit 2 [Day 1] and Visit 3 [Day 28], respectively).

If a participant forgets to take the study drugs on a given day, he/she should take the next dose as normal and should not take a double dose to make up for the forgotten dose.

5.5.4 Treatment Compliance

Compliance with the study drug regimen will be evaluated by counting unused tablets and capsules. Participants will be instructed to bring all unused study drugs to the site at Visit 3 (Day 28) and at Visit 4 (Day 84) (or at an EOT Visit, in cases of early discontinuation of study drug or study). During the Treatment Period, if compliance is not between 80% and 120%, inclusive, the participant will be counselled about the importance of compliance with the regimen.

5.5.5 Storage and Accountability

All study drugs must be stored at room temperature, no higher than 77°F (25°C), and protected from moisture in a secure area with access limited to the Investigator and authorized site personnel.

In accordance with regulatory requirements, the Investigator or designated site personnel must document the amount of study drugs dispensed and/or administered to participants, the amount returned by participants, and the amount received from and returned to the Sponsor (or representative) when applicable. Study drug accountability records must be maintained throughout the course of the study. The accountability unit for this study is a tablet or capsule. Discrepancies are to be reconciled or resolved. At the end of the study, a final reconciliation must be made between the amount of study drug supplied, dispensed, and subsequently returned to the Sponsor (or representative) or destroyed with the written permission of the Sponsor, in accordance with applicable laws and study site's procedures. Procedures for final disposition of unused study drugs will be provided in the appropriate study manual.

5.6 Prior and Concomitant Medications and/or Procedures

5.6.1 Excluded Medications and/or Procedures

Participants must not take any other investigational products or use any investigational devices within 30 days of Screening (Visit 1) or 5 half-lives of the previous investigational product, whichever is longer, or during the course of the study or they will be excluded from study participation.

Participants must not take gemfibrozil within 30 days of Screening (Visit 1) or during study participation. Participants must not take additional ezetimibe within 14 days of Screening (Visit 1) or during study participation. Participants must agree not to donate blood during study participation.

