1.6.1 Coronavirus Disease 2019 Impacts

In March 2020, Coronavirus Disease 2019 (COVID-19), caused by infection with severe acute respiratory syndrome coronavirus 2, was characterized as a pandemic by the World Health Organization (WHO). The COVID-19 pandemic has impacted clinical studies worldwide due to quarantines, site closures, travel limitations, diversion of resources, and/or general interruptions in study-related procedures. This study will be initiated during the ongoing COVID-19 pandemic. The Sponsor has reviewed guidance from regulatory authorities and reports from the literature while planning study start-up and conduct (ie, European Medicines Agency 2022, FDA 2021). 21,22

The Sponsor will communicate with sites before study initiation and during the conduct of the study concerning the potential impact of COVID-19 on study-related procedures and overall conduct. The Sponsor will continue to monitor COVID-19 activity in the geographic areas and institutions where the trial will be conducted and conduct an ongoing risk assessment throughout the study. The risk assessment will be documented on an ongoing basis in the Sponsor's trial master file.

This study protocol includes contingency measures to ensure participant safety while enabling sites to generate reliable data and maintain integrity of the study and study data (see Section 3.1.4). The impacts of these implemented contingency measures on the outcomes of this study, including any protocol deviations that result from COVID-19 illness and/or COVID-19 control measures, will be discussed in the Clinical Study Report.

Treatment with standard of care and/or emergency use authorization medications, including vaccinations and boosters, for COVID-19 will be permitted during this study. There is no known negative impact of vaccination on obicetrapib efficacy and safety, nor any known negative impact of obicetrapib on vaccination efficacy and safety.

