4.5 Withdrawal Criteria

A participant may prematurely discontinue study drug and/or withdraw from the study at any time. However, a distinction must be made between premature discontinuation of study drug and withdrawal from the study. All efforts should be made to ensure the participant continues in the study per protocol. If a participant discontinues study drug prior to completion of the study, all efforts will be made to continue to follow the participant and collect data for all visits.

Only participants that request discontinuation from the study and withdraw consent will be considered withdrawn from the study. For safety reasons, it will be recommended that all participants who withdraw from the study complete an End of Treatment (EOT) Visit. Withdrawn participants will not be replaced.

Participants may need to discontinue study drug during the course of the study. All efforts will be made to restart the study drug; however, in the event of the following, participants may be permanently discontinued from study drug:

- Occurrence of any medical condition or circumstance that exposes the participant to substantial risk and/or does not allow the participant to adhere to the protocol-specified study drug treatment regimen;
- Any SAE, clinically significant AE, severe laboratory abnormality, intercurrent illness, or other medical condition, which indicates to the Investigator that continued treatment with study drug is not in the best interest of the participant;
- Pregnancy; or
- Requirement of prohibited concomitant medication.

If a participant permanently discontinues study drug, he/she will continue to participate in study visits as described below:

- If a participant discontinues study drug between Visit 2 (Day 1) and Visit 3 (Day 28) or at Visit 3 (Day 28), he/she should complete an EOT Visit at Day 28, return to complete Visit 4 (Day 84), and return to complete the Safety Follow-up Visit (Day 112); or
- If a participant discontinues study drug between Visit 3 (Day 28) and Visit 4 (Day 84), he/she should return for Visit 4 (Day 84) and the Safety Follow-up Visit (Day 112) as scheduled.

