9.2.1.1 Primary efficacy analysis

The primary efficacy endpoint is the percent change from Day 1 to Day 84 in LDL-C. Co-primary endpoints include the percent change from Day 1 to Day 84 in LDL-C for the obicetrapib 10 mg + ezetimibe 10 mg FDC treatment group compared with each of the following: placebo, ezetimibe 10 mg monotherapy, and obicetrapib 10 mg monotherapy, and for the obicetrapib 10 mg monotherapy treatment group compared with placebo. The primary endpoint

will be analyzed using an analysis of covariance (ANCOVA) model with a fixed effect for the treatment group and a covariate of baseline LDL-C. The least squares (LS) mean, standard errors, and 2-sided 95% confidence intervals for each treatment group and for the mean difference compared to placebo will be obtained.

Each of the comparisons within the co-primary endpoint family will be conducted at a significance level of 0.05. If and only if all 4 testing achieve statistical significance, the study is claimed to meet its primary objective and the hypothesis testing will continue to secondary endpoints, otherwise all statistical comparisons for secondary endpoints are considered descriptive only.

The primary estimand will correspond to a treatment policy estimand. The target population will comprise participants who are randomized into the study. The primary summary measure to assess the treatment effect will be the LS mean difference for the primary endpoint between obicetrapib 10 mg + ezetimibe 10 mg FDC treatment and placebo, ezetimibe 10 mg monotherapy, and obicetrapib 10 mg monotherapy based on the ANCOVA methodology. The primary estimand will be addressed using the in-study observation period (ie, including data collected post treatment discontinuation or post prohibited medication use).

Missing data will be imputed for the primary efficacy analysis based on a pattern mixture model that uses a multiple imputation technique analyzed with ANCOVA with pre-specified fixed factors and covariates. If appropriate, based on the number of retrieved dropouts, missing measurements of non-retrieved dropouts will be modeled by known measurements from retrieved dropouts (ie, participants who remain in the study after treatment discontinuation) in the same treatment group. The imputation model will be further clarified in the SAP.

Additional sensitivity analyses may be carried out under secondary estimands and/or various assumptions for missing data. Full details will be provided in the SAP.

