3.4.1 Primary Efficacy Endpoints

Primary Analysis

The primary efficacy endpoint is the percent change from Day 1 to Day 84 in LDL-C. Co-primary endpoints include the percent change from Day 1 to Day 84 in LDL-C for the obicetrapib 10 mg + ezetimibe 10 mg FDC treatment group compared with each of the following: placebo, ezetimibe 10 mg monotherapy, and obicetrapib 10 mg monotherapy, and for the obicetrapib 10 mg monotherapy treatment group compared with placebo.

Each of the comparisons within the co-primary endpoint family will be conducted at a significance level of 0.05. If and only if all 4 testing achieve statistical significance, the study is claimed to meet its primary objective and the hypothesis testing will continue to secondary endpoints, otherwise all statistical comparisons for secondary endpoints are considered descriptive only.

The LDL-C values measured by preparative ultracentrifugation (PUC) will be used. If the later measurement is not available, the LDL-C values will be assumed missing.

All the analysis for primary efficacy endpoint will be repeated with LDL-C values calculated as follows:

- 1. LDL-C will be calculated using the Friedewald equation unless triglycerides ≥400 mg/dL or LDL-C ≤50 mg/dL; where, LDL-C level will be measured directly by PUC.
- 2. LDL-C will be calculated using the Martin-Hopkins equation unless triglycerides ≥400 mg/dL or LDL-C ≤50 mg/dL; where, LDL-C level will be measured directly by PUC.

Primary Estimand

To assess the primary efficacy endpoint, the primary estimand is defined by the following key attributes:

- **Treatment**: obicetrapib 10 mg + ezetimibe 10 mg FDC treatment versus placebo, ezetimibe 10 mg monotherapy, and obicetrapib 10 mg monotherapy, and obicetrapib 10 mg monotherapy versus placebo
- Target Population: participants who are randomized into the study
- **Analysis Population**: The ITT Population
- Intercurrent events: treatment discontinuation, prohibited medication use

- **Analysis set and handling of intercurrent events**: Treatment policy strategy will be used. All available values of LDL-C at Baseline and Day 84 will be included in the calculation of the percentage change from Baseline to Day 84.

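### Protocol section 5.6.1, read literally, ends study participation for a randomized participant who takes another investigational product, which conflicts with section 4.5 and the treatment-policy estimand (minor)

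*Protocol*

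**What the plan says.** Protocol section 5.6.1 prohibits other investigational products and devices for 30 days or five half-lives before Screening, whichever is longer, and then continues: "or during the course of the study or they will be excluded from study participation". One consequence is attached to both periods. The gemfibrozil and ezetimibe bans in the same section carry no such consequence.

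Protocol section 4.5 separates stopping study drug from leaving the study. On leaving, it says: "Only participants that request discontinuation from the study and withdraw consent will be considered withdrawn from the study". "Requirement of prohibited concomitant medication" is on its list of circumstances in which study drug may be stopped permanently. It then says: "If a participant permanently discontinues study drug, he/she will continue to participate in study visits as described below", and the schedule that follows runs to Visit 4 (Day 84) and the Safety Follow-up Visit (Day 112). It also says: "Withdrawn participants will not be replaced".

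Protocol section 9.2.1.1 defines a treatment-policy primary estimand based on all in-study observation, "including data collected post treatment discontinuation or post prohibited medication use". SAP section 3.4.1 lists the intercurrent events as "treatment discontinuation, prohibited medication use", applies the treatment policy strategy, and uses every available baseline and Day 84 LDL-C value.

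**The concern.** Before randomization, excluding someone who has used another investigational product is an ordinary eligibility rule. After randomization, the same words tell a site to end a participant's involvement because of something that happened on study. Section 4.5 does not allow that route out of the study, and the estimand needs the value that would then not be measured.

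What is at stake is the Day 84 LDL-C of any participant handled this way. Follow-up to Day 112 could be lost too, although Protocol section 8.1 monitors adverse events until that visit is complete.

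**Working it through.** **1. The plan's own figures.** Inputs from Protocol section 9.2.4: 95 evaluable per arm, SD 25, one-sided alpha 0.025, and differences of 30, 20, 12 and 15 points.

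- SE of a difference = 25 × √(2/95) = 3.63 points.
- Power = Φ(difference/SE − 1.96).
- 30 points: above 99.9%. 20 points: 99.98%. 15 points: 98.5%. 12 points: Φ(12/3.63 − 1.96) = 91.1% (90.8% by noncentral t).
- Randomized per arm = 95/0.95 = 100, or 400 in total.

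The stated power of more than 90% for each comparison and the enrolment of about 400 both reproduce. The point does not arise from the sample size.

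**2. The passages side by side, for a randomized participant who takes another investigational product on, say, Day 40.**

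- Section 5.6.1, read literally: participation ends.
- Section 4.5: the participant has not withdrawn consent, so has not left the study. Study drug may or may not be stopped. Visits 4 and 5 go ahead either way.
- Section 9.2.1.1 and SAP section 3.4.1: the Day 84 value, taken after the event, is used.

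The second and third agree with each other, and the first does not fit either. No other section reconciles them. Neither document defines prohibited medication by a list under that name. I take section 5.6.1 to supply it, since its heading is the list of excluded medications.

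**3. What happens to the data.** Both documents define the ITT Population as everyone randomized, so the participant stays in it. If Day 84 is missing, SAP section 3.4.1 imputes it from participants in the same arm who stopped treatment but were still measured. If too few of those exist for the model to be fitted, it imputes from placebo. Neither source is a good match for someone who may have been taking study drug until removal. One partial substitute exists: SAP section 3.1.2 assigns an early-termination visit on analysis Days 57 to 98 to Day 84. Section 5.6.1 does not say whether an excluded participant attends such a visit.

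The secondary, hypothetical estimand does not need removal either. SAP section 3.4.1 sets aside values after prohibited medication at the analysis stage.

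**4. Size.** The documents give no rate of on-study use, so I assume 0 to 2 per 100 per arm. The shift in an arm mean per case is the change in that participant's value divided by 100.

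- FDC participant still on drug, value replaced by a placebo-like one, using the planned 30-point difference: 30/100 = 0.30 points, or 0.30/3.63 = 0.08 SE. This shrinks the FDC effect.
- Placebo participant whose LDL-C fell 50% on another agent (assumed), value lost: 50/100 = 0.50 points, or 0.50/3.63 = 0.14 SE. This enlarges the effect against placebo.
- Two such cases in an arm: 0.6 or 1.0 points, against a smallest planned difference of 12.
- If each case is instead counted as one fewer evaluable participant per arm, power for the 12-point comparison is 91.1% at 95, 90.8% at 94 and 90.5% at 93. It falls below 90% at 91 (89.9%), which is outside the assumed range.

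**The case against.** The strongest reply is that section 5.6.1 only restates eligibility. Its first half tracks exclusion criterion 12 and its second half resembles exclusion criterion 15. Its closing words echo the lead-in to section 4.2 rather than the withdrawal and discontinuation terms of section 4.5. On that reading, section 4.5 is the dedicated rule after randomization and already gives the right answer.

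This is plausible, and it may be what was meant. It does not remove the conflict, because criterion 15 covers only planned use, while section 5.6.1 forbids actual use while the study is running. Section 5.6.2 shows how the protocol words an on-study rule when it means one: changes to lipid-modifying therapy are recorded and reported as deviations, with no removal.

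Several stronger readings are tempting, and the documents do not support them:

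- A reader might infer that Day 84 data are removed from the analysis. They are not: the SAP deletes no collected value, and a loss occurs only if a site applies 5.6.1 over 4.5 before Day 84.
- A reader might infer a bias in favour of study drug. The two worked cases point in opposite directions, and the placebo-like replacement in the first arises only under the fallback imputation.
- A reader might extend the problem to all prohibited medication. The wording reaches only investigational products and devices.
- A reader might think COVID-19 treatments trigger exclusion. Section 1.6.1 says that standard-of-care and "emergency use authorization medications, including vaccinations and boosters, for COVID-19 will be permitted during this study", and the note to exclusion criterion 12 covers the period before Screening.

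**Conclusion.** Wrong as written, minor. Section 5.6.1 attaches the end of study participation to an event after randomization, and this cannot be squared with section 4.5 or with the treatment-policy estimand. The practical risk is a Day 84 LDL-C left uncollected and then imputed. That requires a participant to take another investigational product during a 12-week treatment period, and a site to follow 5.6.1 rather than 4.5.

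Few participants are likely to be affected. On the assumed frequency and effect sizes, each case is worth about 0.1 standard error of a treatment difference. That would be unlikely to alter a co-primary result unless it were already close to the significance boundary. The conflict itself rests on the wording alone and does not depend on those assumptions.

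**What to change.** Reconcile section 5.6.1 with section 4.5 and the estimand by splitting the sentence.

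- Limit exclusion to eligibility before randomization, with reference to exclusion criteria 12 and 15.
- State that use of another investigational product or device after randomization is recorded as a protocol deviation and as an intercurrent event, and that Day 84 and Day 112 data are still collected under section 4.5.
- Leave any consequence for study drug to the sponsor's reconciliation of the two sections. This review does not propose one.
- Optionally, add a cross-reference to the COVID-19 permission in section 1.6.1.

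The cost is one protocol sentence. No participants, visits or analyses are added, and the SAP text on intercurrent events can stand.
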